### **3.5 Conduct of the Study**

#### **3.5.1 Screening Procedures and Patient Enrollment Prior to Catheterization**

All patients admitted for percutaneous revascularization should be assessed for potential study eligibility.

#### **3.5.2 Catheterization and Stenting Procedure**

The stenting procedure will follow standard procedures for balloon angioplasty and shall be in accordance with the Instructions for Use packaged with each DESyne X2 stent. The available stent diameters are 2.25 mm, 2.75 mm, 3.0 mm, 3.5 mm, and 4.0 mm with stent lengths of 14 mm, 18 mm, 23 mm, 28 mm, 32 mm, and 38 mm lengths. Pre-dilate the lesion using a balloon that is shorter in length than the planned DESyne X2 stent length. Deploy the stent slowly until the stent is completely expanded. Maintain pressure for 30 seconds. Direct stenting is not recommended.

- Should any resistance be felt at any time during either lesion access or removal of the delivery system post stent implantation, the entire system should be removed as a single unit (See appropriate IFU for further information).
- According to the IFU, stent expansion should not exceed the RBP of 16 atm and the stent should not be expanded beyond 0.5 mm over the nominal diameter.

Evaluate the lesion via angiography. If an optimal angiographic result has still not been achieved using the coronary stent system, additional balloon inflations using an appropriately sized, non-compliant balloon may be performed.

[figure not shown]
The stenting procedure will include a single lesion treatment in a single epicardial vessel or a single lesion treatment in up to three separate major epicardial territories.

Maintain a copy of all of the index procedure angiographic images for possible analysis by an independent angiographic core laboratory.

---

 Not all sizes available in all regions. Subject to commercial availability. Availability is based on regulatory and hospital approvals.

### Flowchart for Treatment of Two Lesions in Two Separate Epicardial Territories

#### Optimal lesion/vessel treatment is defined as:

- a. < 20% residual stenosis by visual assessment
- b. no evidence of dissection
- c. no evidence of thrombus in the target lesion or vessel
- d. TIMI 3 flow

#### 3.5.3 Bailout Procedures

In the event that a patient experiences a dissection or an occlusive complication or if there is incomplete lesion coverage, further stenting may be employed as a bailout treatment using a DESyne X2 stent or other commercially available stent of the same metal composition and the same drug family. The stents should overlap by at least 1-2 mm.

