#### 3.5.4 Treatment Failures

Failure to implant the DESyne X2 stent at the intended target site will be recorded as a treatment failure on the case report form. In the event of the inability to treat the lesion with the study stent, the physician may treat the patient according to his/her medical judgment with another approved device. These patients should receive standard antiplatelet therapy.

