### 3.5.7 Other Follow-up Guidelines

There may be situations where an attempt to treat the patient with the DESyne X2 stent is made, but the procedure is stopped prior to the stent being delivered to the target site (i.e., the stent is introduced into the guiding catheter and circulation but patient becomes unstable, power outage, etc.). In these situations, the patient will be deregistered from the study and treated per standard hospital practice.

In the situation where an attempt to treat the patient with the DESyne X2 stent is made but due to a device malfunction or failure to cross the lesion, no DESyne X2 stent is subsequently implanted, the case shall be noted as not meeting the Device Success endpoint. All device failures will be recorded and reported.

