## 4.0 ENDPOINTS

The following endpoints chosen for the post market clinical follow-up evaluation are the recognized professional and industry standards in determining performance of drug eluting stents in interventional cardiology.

- Acute Device Success: attainment of final result with < 50% residual stenosis of the target site, using a DESyne X2 stent and standard pre-dilation catheters and post-dilatation catheters (if applicable)

Physician feedback will be obtained for the following device characteristics:

- Device preparation
- Lesion access and cross
- Stent expansion
- Delivery system removal
- Stent crossability for post-dilatation as required
- Device malfunction assessment

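### Device Success is met when a second X2 system rescues a failed first one, and can be read as met after other-brand bailout, so the main performance rate is insensitive to first-system delivery failure

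*Combined protocol and SAP*

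**What the plan says.** Device Success has the same core definition in Sections 1.0, 2.6, 4.0 and 9.0. In Section 4.0 it is "attainment of final result with < 50% residual stenosis of the target site, using a DESyne X2 stent and standard pre-dilation catheters", plus post-dilatation catheters where used. Four other rules bear on it:

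- **Section 3.5.7** covers the case where "due to a device malfunction or failure to cross the lesion, no DESyne X2 stent is subsequently implanted"; then "the case shall be noted as not meeting the Device Success endpoint". The same section adds: "All device failures will be recorded and reported". Attempts stopped before delivery for reasons such as patient instability or a power outage are deregistered.
- **Section 3.5.4:** "Failure to implant the DESyne X2 stent at the intended target site will be recorded as a treatment failure on the case report form".
- **Section 3.5.3** permits bailout stenting for dissection, an occlusive complication or incomplete coverage, "using a DESyne X2 stent or other commercially available stent of the same metal composition and the same drug family". It does not mention Device Success.
- **Section 6.0** analyses one population, MITT, made up of patients treated with at least one X2 stent. Categorical endpoints are given as patient counts and percentages with exact 95% Clopper-Pearson intervals.

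Section 4.1 has sites record the number of stents, the stent brand, and details of implantation success or malfunction.

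**The concern.** Section 2.2 names the delivery system as the main difference between X2 and the earlier devices. Section 2.3 ties the study's questions, lesion access and acute implantation, to that delivery system. A failure of the first X2 system to cross or deploy is therefore the event of most interest.

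Device Success is judged on the final state of the lesion. It does not record how many systems were needed to get there, or clearly whether every implanted stent was an X2. Such cases are foreseeable: Section 3.5.2 describes removing the whole system when resistance is felt, and Section 3.5.3 provides for bailout.

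The other listed characteristics (preparation, access and crossing, expansion, removal, crossability, malfunction) are collected as physician feedback and have no stated success criterion. Device Success is the only rate with a numerical threshold, and so the natural headline figure against historical DESyne data. If it cannot fall when a first system fails, a favourable rate says little about the question the study asks.

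**Working it through.** **Step 1. Score each situation against the text.** Residual stenosis is taken as below 50% unless stated.

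| Situation | Device Success as worded | Basis |
|---|---|---|
| Residual stenosis 50% or more | Fails | Definition |
| No X2 implanted, another brand only | Fails | Definition; also 3.5.4, and 3.5.7 if due to malfunction or failure to cross |
| First X2 system fails, second X2 implanted | Met | Definition asks for an X2 stent, not the first; the 3.5.7 failure rule does not apply because an X2 was implanted later |
| X2 implanted, finished with other-brand bailout stent | Unclear | An X2 stent was used, but the list of an X2 stent and dilatation catheters can also be read as exhaustive |

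The third row follows from the wording. The fourth has two defensible readings and no rule to choose between them.

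**Step 2. Check the denominator.** A patient with no X2 implanted fails Device Success under Section 3.5.7 when the cause is malfunction or failure to cross. Section 6.0 then leaves that patient out of MITT. Read literally, the clearest failure drops out of the rate.

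**Step 3. Size.** The plan gives no rate, margin or expected count for Device Success, so there is no planned figure to reproduce. The counts below are assumptions: 100 attempts, one lesion per patient, 1 non-implant, 3 rescues, all others clean. Intervals are exact Clopper-Pearson, the method in Section 6.0. When x = n the lower limit is 0.025^(1/n). Otherwise the limits are the 2.5% quantile of Beta(x, n−x+1) and the 97.5% quantile of Beta(x+1, n−x).

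- As written: n = 100 − 1 = 99, all successes. 99/99 = 100%; lower limit 0.025^(1/99) = 96.3%. Interval 96.3–100%.
- Rescues counted as failures, MITT kept: 99 − 3 = 96; 96/99 = 97.0% (91.4–99.4%).
- Non-implant also restored: 96/100 = 96.0% (90.1–98.9%).

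Of the four-point gap, about three points come from scoring the rescues and one from the denominator.

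The 96/100 figure pools both kinds of rescue. If two of the three were replacement X2 systems and one was an other-brand finish after a clean first delivery:

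- First-system success: 100 − 1 − 2 = 97/100 (91.5–99.4%).
- X2-only success: 100 − 1 − 1 = 98/100 (93.0–99.8%).

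**Step 4. Range over the unknown number of rescues.** Take 100 MITT patients, one lesion each, all ending below 50% with an X2 in place. Counting rescues as successes always gives 100/100 (96.4–100%). Counting them as failures gives:

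| Rescued | Rate | Exact 95% interval |
|---|---|---|
| 1 | 99% | 94.6–100.0% |
| 2 | 98% | 93.0–99.8% |
| 3 | 97% | 91.5–99.4% |
| 5 | 95% | 88.7–98.4% |
| 10 | 90% | 82.4–95.1% |

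Each rescue moves the rate by one point when there are exactly 100 units. With up to three lesions per patient, the step depends on whether patients or lesions are counted.

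**The case against.** The strongest reply is that this is a descriptive study with no test, margin or success threshold, and that delivery failures are captured elsewhere. Section 3.5.7 has all device failures recorded and reported, and access, crossing, removal and malfunction are listed among the key endpoints in Section 1.0. That stands: a reader might infer that the plan hides delivery failures, and it does not. What is missing is any rule linking those records to Device Success, or a defined rate built from them.

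Three other stronger readings also fail:

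- *Device Success fails only when no X2 is implanted.* The documents do not say so, and residual stenosis of 50% or more also fails.
- *Any lesion rescued with another brand counts as an X2 success.* A lesion treated solely with another brand does not meet the definition. The question arises only when an X2 is also in place.
- *Section 3.5.7 tells analysts to score every other case as a success.* It names one failing situation and does not classify the rest. The replacement-X2 result comes from that rule's silence together with the definition itself.

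A further fair point concerns comparability. Section 9.0 presents the acute success categories as benchmarks between similar treatments, and the historical DESyne definition is not in the documents. Tightening Device Success on the X2 side alone could bias the comparison. This is a good reason to add measures and leave the existing one in place. It is no reason to leave the gap.

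**Conclusion.** The point holds in a limited form. A lesion saved by a second X2 system meets Device Success as worded, and an X2 finished with an other-brand stent can be read as meeting it. The failures are reported separately, but the only rate with a numerical criterion is insensitive to first-system delivery failure, and the MITT rule can also remove non-implants from it.

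In the illustration the difference is 99/99 (96.3–100%) against 96/100 (90.1–98.9%). It rests on assumed counts and one lesion per patient. The documents give no expected frequency of replacement or bailout, so the true effect could be nil or larger. No figure in the plan is contradicted. The change should be made, because with few failures expected the counting rule could account for most of the observed shortfall from 100%.

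**What to change.** 1. Keep Device Success as defined for the historical DESyne comparison. In Sections 2.6, 4.0 and 9.0, state that a lesion whose final result includes a non-X2 stent is not an X2-only success, and show the rate both ways.
2. Add a per-lesion first-system success rate: first X2 system delivered, deployed and withdrawn without malfunction or replacement.
3. Add the bailout rate.
4. In Section 6.0, compute the rates in items 2 and 3, each with an exact 95% interval, over all lesions in which an X2 system was introduced, apart from attempts stopped for non-device reasons under Section 3.5.7. Non-implants then stay in the denominator.

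Item 2 is needed alongside item 1, because an X2-only rule would still pass a lesion rescued by a replacement X2. The data are already recorded under Section 4.1, so the cost is definition wording, a little more analysis and probably a slightly less favourable rate. Bailout practice itself is not affected.

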#### 3.5.4 Treatment Failures

Failure to implant the DESyne X2 stent at the intended target site will be recorded as a treatment failure on the case report form. In the event of the inability to treat the lesion with the study stent, the physician may treat the patient according to his/her medical judgment with another approved device. These patients should receive standard antiplatelet therapy.

#### 3.5.5 Concomitant Medical Therapy

It is recommended that all patients receive dual antiplatelet therapy including aspirin and aP2Y12 inhibitor for at least one year as currently recommended by the AHA/ACC guidelines and hospital standards.

### 3.5.6 Clinical and Laboratory Procedures

It is recommended to perform an electrocardiogram and cardiac enzymes be assessed prior to the procedure and post-procedure as per hospital standard.

### 3.5.7 Other Follow-up Guidelines

There may be situations where an attempt to treat the patient with the DESyne X2 stent is made, but the procedure is stopped prior to the stent being delivered to the target site (i.e., the stent is introduced into the guiding catheter and circulation but patient becomes unstable, power outage, etc.). In these situations, the patient will be deregistered from the study and treated per standard hospital practice.

In the situation where an attempt to treat the patient with the DESyne X2 stent is made but due to a device malfunction or failure to cross the lesion, no DESyne X2 stent is subsequently implanted, the case shall be noted as not meeting the Device Success endpoint. All device failures will be recorded and reported.

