### 4.1 Lesion, vessel, and stent characteristics

Lesion, vessel, and stent characteristics recorded in the source documentation should include:

- Estimated reference vessel diameter (target lesion)
- Estimated lesion length
- Estimated % DS (target lesion)

- Number of stents used
- Stent brand
- Vessel (LAD, LCX, RCA, Left Main)
- Lesion location (ostial, proximal, mid, distal, branch)
- Stent diameter (mm)
- Stent length (mm)
- Lot number of the DESyne X2 stent
- Success of stent implantation or device malfunction details

**Note:** Maintain a copy of all of the index procedure angiography for possible analysis by an angiographic core laboratory.

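### Patients in whom the X2 system was introduced but no X2 stent was implanted drop out of the Device Success rate, through the MITT definition in Section 6.0 and the deregistration clause in Section 3.5.7

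*Combined protocol and SAP*

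**What the plan says.** Five places in the protocol bear on a patient whose delivery attempt does not end with an X2 stent in place.

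- **Section 5.0** sets enrolment at the introduction of the intended device into the body. It then names two ways out: withdrawal of consent, or withdrawal by the physician.
- **Section 3.5.7, first paragraph**, covers attempts stopped before the stent reaches the target site. One example is that "the stent is introduced into the guiding catheter and circulation but patient becomes unstable"; another is a power outage, and the list is left open. The consequence is "In these situations, the patient will be deregistered from the study and treated per standard hospital practice".
- **Section 3.5.7, second paragraph**, covers device malfunction or failure to cross when no X2 stent is then implanted: "the case shall be noted as not meeting the Device Success endpoint". It adds "All device failures will be recorded and reported".
- **Section 3.5.4** gives a recording rule that does not depend on cause: "Failure to implant the DESyne X2 stent at the intended target site will be recorded as a treatment failure on the case report form".
- **Section 6.0** names a single analysis population, the MITT, made up of patients treated with one or more X2 stents. Results are descriptive, with exact Clopper-Pearson 95% intervals, and are set beside the EXCELLA II results. No margin or target rate is given.

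**The concern.** The study asks about lesion access and acute implantation, and Section 2.3 says these are the attributes most closely tied to the updated delivery system. A patient in whom the system went in and no X2 stent came to be implanted is therefore highly informative. Two rules take such patients out.

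First, the MITT leaves out anyone with no X2 stent. That includes the malfunction and failure-to-cross cases that Section 3.5.7 classes as not meeting Device Success. The protocol defines a failure and then analyses a population in which that failure cannot occur.

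Second, Section 3.5.7 deregisters some patients whom Section 5.0 has already enrolled, on a cause assigned after the attempt. No sentence says which paragraph governs when both fit. The protocol makes such a case foreseeable. Section 3.5.2 begins an instruction with "Should any resistance be felt at any time during either lesion access or removal of the delivery system" and has the whole system withdrawn. If the patient then becomes unstable and the procedure ends, both paragraphs describe the case.

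At stake are the reported Device Success rate and the completeness of the device-failure record.

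**Working it through.** **Step 1. Set the rules side by side for a patient with no X2 stent implanted.**

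| What happened after introduction | Section 5.0 | Section 3.5.7 | Section 3.5.4 | Section 6.0 MITT |
|---|---|---|---|---|
| Malfunction or failure to cross | enrolled | not a Device Success | treatment failure | left out |
| Stop for a non-device reason | enrolled | deregistered | treatment failure, on its wording | left out |
| Resistance, then instability, then stop | enrolled | either paragraph fits | treatment failure | left out |

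Row 1 shows the main defect: the status given by Section 3.5.7 has no denominator in Section 6.0. Rows 2 and 3 show that deregistration does not alter the planned rate for these patients, because the MITT leaves them out anyway. In row 3, deregistration can alter whether the case is recorded as a device failure.

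**Step 2. Formulas.** Let S be successes, I non-successes with an X2 stent implanted, D malfunction or failure-to-cross cases with no X2 stent, and K other stops with no X2 stent. Introductions are N = S + I + D + K.

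- Plan as written (MITT): S / (S + I)
- Device failures counted: S / (S + I + D)
- All stops also counted as non-successes: S / N

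Whenever S and D are both at least 1, the first rate exceeds the second, so the direction of the bias does not depend on the counts chosen. K appears only in the third.

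**Step 3. Numbers.** The plan states no Device Success rate to reproduce and no expected number of failures or stops. The inputs are assumed: N = 100 (the enrolment ceiling, used here as introductions), S = 95, I = 0, D = 2, K = 3. Intervals are exact Clopper-Pearson 95%, the method named in Section 6.0.

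| Analysis | Rate | 95% interval |
|---|---|---|
| MITT | 95/95 = 100% | 96.2 to 100 |
| Device failures counted | 95/97 = 97.9% | 92.7 to 99.7 |
| All stops also non-successes | 95/100 = 95.0% | 88.7 to 98.4 |

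For 95/95 the lower limit is 0.025^(1/95) = 0.962.

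**Step 4. Attribute the difference.** The fall from 100% to 97.9% (2.1 points) comes from the MITT definition alone. The further fall to 95.0% (97.9 − 95.0 = 2.9 points) is the most that deregistration could account for, and only once the population is widened. If one of the three stops followed a delivery problem and counts as a device failure, the rate is 95/98 = 96.9% (91.3 to 99.4). If two did, it is 95/99 = 96.0% (90.0 to 98.9). If none did, deregistration accounts for nothing and the rate stays at 97.9%.

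**The case against.** **No stated decision changes.** Section 6.0 is descriptive and has no margin. This stands. It limits the consequence to the reported estimate and its interval, but those are what the study delivers.

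**The protocol already directs much of the recording.** Section 3.5.7 promises that device failures are reported and makes no exception for deregistered patients. Section 3.5.4 records failures to implant. Sections 2.6 and 4.0 collect physician feedback on lesion access and malfunction. Section 7.3 keeps issue and deviation logs, and Section 8.1.2 asks for notes on device performance. This also stands: the information may well exist at the site. It does not give the failures a denominator, and it does not say how a mixed case is classed. Section 4.1 lists "Success of stent implantation or device malfunction details" but no reason for stopping. The case report form is not in the documents, so it may hold that item.

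**The stop examples are all non-device causes**, so the open end of the list can be taken to mean similar causes. That is a fair reading of the clear cases. It does not settle a stop that follows resistance.

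**Readings that go too far.** A reader might infer that Sections 3.5.7 and 5.0 flatly contradict each other. They do not have to: deregistration can be read as withdrawal by the physician, and the sentence on exits in Section 5.0 is incomplete. It is a tension and a missing link. A reader might also infer that deregistration itself inflates the planned rate. For a patient with no X2 stent it does not, because the MITT has already left that patient out. Nor do the documents show that device failures would be misclassified; they show only that the boundary is open. The share of mixed-cause cases is not given, so no loss of ability to detect rare problems can be calculated.

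**Conclusion.** The point holds. As written, the plan cannot count malfunction or failure to cross with no X2 stent implanted as a Device Success failure, although Section 3.5.7 says it is one. The rate is therefore biased upward whenever such a case occurs. The MITT definition drives this. The deregistration clause would add to it only after the population is widened. Under the current plan it matters mainly for whether a mixed-cause stop reaches the record of device failures.

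The direction follows from the text, but the size is unknown. In the illustration the gap is 2.1 points for two device failures, with up to 2.9 more for three stops. These figures rest wholly on assumed counts, with one outcome per patient and no non-successes among implanted patients. The effect on the comparison with EXCELLA II cannot be judged, because the protocol does not give that study's acute success rate or the population behind it.

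**What to change.** **Section 6.0.** Analyse Device Success in patients in whom the X2 system was introduced. In the main result, count malfunction and failure to cross as non-successes, including stops that followed a delivery problem, and leave out only stops with a documented non-device cause. As a sensitivity result, count those documented non-device stops as non-successes too. List every stopped attempt with its reason. State in advance where a stop with no documented cause falls; treating it as a non-success is the cautious choice.

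**Sections 3.5.7 and 5.0.** Cross-refer them. State that neither deregistration nor physician withdrawal after introduction removes acute procedural and adverse-event data already collected, unless consent is withdrawn.

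**Section 3.5.4.** Align the case report form entry with the Section 3.5.7 classification.

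**Cost.** Wording in four sections, one extra rate, one listing, and a stop-reason item if the case report form lacks one. The reported rate may be about 1 point lower for each retained failure in 100 introductions (1/100). This is data handling only; patient care is unchanged.
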